4.2.2 Temperature stability and regulation

Hourly record of temperatures displayed on the incubator:

- the actual incubator temperature
- set temperature of the incubator
- Core/truncal temperature (from vital signs monitor/skin probe)

4.2.3 Usability

Time to clean each incubator type between/after use.

4.2.4 Adverse events

ADE and SADEs assessed.

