3.2 Secondary objectives

Assessment of:

- Comparability to maintain clinical stability by measurement of physiological parameters.
- The mOm incubators ability to maintain and regulate its temperature to within the appropriate BS standard⁵ in clinical practice.
- Comparison of between subject cleaning times.
- Incubator performance related adverse events.
- Staff feedback on the experience of using the mOm incubator (*i.e.* usability) will also be collected.

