7. ADVERSE EVENTS

7.1 Adverse event (AE)

Any undesirable clinical occurrence in a subject, whether considered to be procedure related or not, that includes a clinical sign or symptom. Typical AEs which should be recorded include but are not limited to: skin injury or infection, pressure sores, hyperthermia, hypothermia, apnea and bradycardia. AEs also include Adverse Device Events (ADEs). ADEs are any undesirable device related event, whether clinically relevant to the subject or not. Typical device ADEs which should be recorded include but are not limited to: rainout, practical access issues, degradation of part of the incubator, inadvertent displacement of lines thought to be due to the design of the incubator.

AEs will be recorded from the time the subject has been enrolled and placed in the first incubator type until the end of their participation in the study (*i.e.* after 48 hours incubation is complete), unless a device related adverse event is on-going in which case it will be monitored until resolved. All AEs should be recorded in the patient notes, the CRF and on the Adverse Event log in the ISF.

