7.2 Anticipated Adverse Event

Any undesirable clinical occurrence in a subject that may be expected to occur during routine care. These will not be reported unless thought to be study related.

Anticipated adverse events may include but are not limited to:

- Reflux
- Wind
- Nappy rash
- Crying

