Not related:	Relationship to the device, comparator or procedures can be excluded when: 
 the event has no temporal relationship with the use of the investigational device, or the procedures related to application of the investigational device the serious adverse event does not follow a known response pattern to the medical device (if the response
---------------------	---

	
pattern is previously known) and is biologically implausible;
 
 • the discontinuation of medical device application or the reduction of the level of activation/exposure - when clinically feasible – and reintroduction of its use (or increase of the level of activation/exposure), do not impact on the serious adverse event; • the event involves a body-site or an organ that cannot be affected by the device or procedure; • the serious adverse event can be attributed to another cause (e.g. an underlying or concurrent illness/ clinical condition, an effect of another device, drug, treatment or other risk factors); • the event does not depend on a false result given by the investigational device used for diagnosis⁹, when applicable; 
In order to establish the non-relatedness, not all the criteria listed above might be met at the same time, depending on the type of device/procedures and the serious adverse event.

Possible:
	
The relationship with the use of the investigational device or comparator, or the relationship with procedures, is weak but cannot be ruled out completely. Alternative causes are also possible (e.g. an underlying or concurrent illness/ clinical condition or/and an effect of another device, drug or treatment). Cases where relatedness cannot be assessed, or no information has been obtained should also be classified as possible.

Probable:
	
The relationship with the use of the investigational device or comparator, or the relationship with procedures, seems relevant and/or the event cannot be reasonably explained by another cause.

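### The adverse event outcome is limited to device-related events, and no summary of all recorded adverse events by incubator is planned

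*Combined protocol and SAP*

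**What the plan says.** - **Objective and outcome.** Section 3.2 lists "Incubator performance related adverse events" among the secondary objectives. The whole of section 4.2.4 reads "ADE and SADEs assessed".
- **Definitions.** Section 7.1 states that "ADEs are any undesirable device related event, whether clinically relevant to the subject or not". It defines AEs more widely, as undesirable clinical occurrences "whether considered to be procedure related or not, that includes a clinical sign or symptom".
- **Recording.** Section 7.1 continues: "Typical AEs which should be recorded include but are not limited to: skin injury or infection, pressure sores, hyperthermia, hypothermia, apnea and bradycardia". Recording runs from placement in the first incubator "until the end of their participation in the study (*i.e.* after 48 hours incubation is complete", so it spans both periods.
- **Anticipated events.** Section 7.2 gives an open-ended list of events expected in routine care and says "These will not be reported unless thought to be study related".
- **Serious events.** Section 7.3 gives SAE and SADE a single shared definition, with no requirement that a SADE be device related.
- **Analysis.** Section 8 does not mention adverse events. It says only that secondary outcomes are presented in the same way as the temperature results.

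**The concern.** Every baby spends 24 hours in each incubator in random order. Adverse events can therefore be compared within baby without any opinion on what caused them. The plan instead makes the outcome depend on a judgement of device relatedness, in a setting where the incubator type is visible. It names no assessor, describes no masking, and does not say whether possible, probable or causal in Table 3 makes an event an ADE. Section 7.4 uses possible device relatedness as a trigger for reporting serious events to the regulator, but does not make it the ADE threshold.

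Such a filter can err in two directions. Events with a plausible background cause may be put down to prematurity, which would hide a real excess in the mOm incubator. Alternatively, staff may blame an unfamiliar device more readily, which would create an excess that is not there. The study hypothesis (section 2) is that the mOm incubator performs as well as a standard one, so either error bears on the safety half of that conclusion.

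**Working it through.** **1. What reaches a comparison, by type of event**

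- Temperature outside 36.5 to 37.5 °C at an hourly reading: yes, through the primary endpoint (section 8).
- Abnormal pulse, respiration or saturation at an hourly reading: yes, through the secondary outcomes (section 4.2.1, Table 1).
- Apnoea or bradycardia between hourly readings, skin injury, pressure sores: recorded under section 7.1, but compared only if classed as ADEs.
- Serious events: unclear, because section 7.3 does not separate SAE from SADE.

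**2. The plan's own figure**

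The only precision figure is ±0.33 degree for mean temperature fluctuation with 36 babies. With an assumed SD of 1 degree (the plan states none), 1.96 × 1/√36 = 0.327, so it reproduces. It has no bearing on adverse events, for which no rate or precision is given.

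**3. What the filter could do**

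The event and attribution rates are assumptions, with at most one event per baby per period. Counted events = 36 × true risk × proportion attributed to the device.

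- *Spurious excess.* True risk 20% in both: 36 × 0.20 = 7.2 events each. Attribution 50% (mOm) v 10% (standard): 7.2 × 0.5 = 3.6 v 7.2 × 0.1 = 0.72, a five-fold ratio where no difference exists. At 30% v 10% it is 2.16 v 0.72, three-fold.
- *Hidden excess.* True risk 20% (mOm) v 10% (standard): 7.2 v 3.6 events. The chance that no mOm-period event is counted is (1 − 0.20 × attribution)^36:

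| Attributed, both incubators | Counted, mOm v standard | Chance of no mOm event counted |
|---|---|---|
| 10% | 0.72 v 0.36 | 0.98^36 = 48% |
| 30% | 2.16 v 1.08 | 0.94^36 = 11% |
| 50% | 3.6 v 1.8 | 0.90^36 = 2% |

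**4. What an all-cause comparison could show**

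For 36 pairs, with periods assumed independent within baby, the 95% half-width for the risk difference is 1.96 × √[(p₁(1−p₁) + p₂(1−p₂))/36]. Power is for the exact McNemar test.

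| Assumed 24-hour risks | Half-width (points) | Power |
|---|---|---|
| 5% v 10% | 12.1 | 3% |
| 10% v 20% | 16.3 | 13% |
| 10% v 30% | 17.9 | 45% |
| 20% v 40% | 20.7 | 36% |

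At least six discordant pairs, all in one direction, are needed for p < 0.05: 2 × 0.5^6 = 0.031, whereas five give 2 × 0.5^5 = 0.0625. If no event of a given type is seen in 36 babies, the one-sided 95% upper bound on the risk is 1 − 0.05^(1/36) = 8.0%.

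**The case against.** The outcome matches its stated objective, in an analysis that section 8 calls largely descriptive. Widening it is better practice rather than the repair of an internal contradiction. That stands.

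Three stronger readings are tempting, and the documents do not support them:

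- A reader might infer that hypothermia, apnoea and bradycardia never enter any comparison of the two incubators. Temperature departures at hourly readings are compared as the primary endpoint. Hourly pulse, respiration and saturation are secondary outcomes. A clinical event judged device related also counts as an ADE, so such events are filtered, not excluded.
- A reader might infer that Table 3 rules out standard-incubator events by construction, since one criterion for an unrelated event is that "the event has no temporal relationship with the use of the investigational device, or the procedures related to application of the investigational device". That row opens by covering the comparator too, as do the possible, probable and causal levels. The possible level also keeps events that have competing causes or cannot be assessed. An event before any mOm exposure is correctly unrelated to mOm.
- A reader might infer that only unmasked ward staff decide what is counted, serious events included. That staff can see the incubator is a fair inference, but no assessor is named. The shared definition in section 7.3 leaves it open whether serious events are filtered at all.

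It is also fair to object that 36 babies are too few to test a difference in adverse events. That is correct and limits what the fix can claim, but a descriptive all-cause table is still more informative than the same few events after filtering.

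**Conclusion.** The concern holds in a limited form. Non-serious clinical adverse events that hourly readings do not capture are recorded in both randomised periods, yet have no planned comparison as events unless judged device related. The rule for that judgement is incomplete: there is no assessor, masking or relatedness threshold.

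The size cannot be fixed from the documents. Under the assumed rates above, the filter could turn no difference into a three- to five-fold ratio, or leave a doubled risk with between a 2% and a 48% chance of showing no mOm event at all. Neither direction is established. The primary temperature comparison is not affected. This is a specific and cheap improvement, not a flaw that invalidates the design.

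**What to change.** - **Sections 4.2.4 and 8.** Tabulate all AEs and SAEs, regardless of causality, by the incubator in use at onset, for every baby placed in a study incubator, including those withdrawn. Give the number of babies with at least one event, event counts, and the within-baby risk difference with 95% CI. Babies observed in one period only appear in the counts but cannot contribute to the within-baby difference; state this. Label the comparison descriptive.
- **Subset.** Show ADEs and SADEs as a subset. State which Table 3 level makes an event an ADE and who decides, and separate SAE from SADE in section 7.3.
- **Onset time.** Require AE onset time on the CRF and AE log. Table 1 specifies start and end times for care events such as door opening, but the plan does not state them for AEs. Incubator identity at the start and at cross-over is already recorded.
- **Section 7.2.** Reconcile the rule on anticipated events with the all-cause table. Otherwise a second relatedness filter remains. Section 6.2, which mentions CRF and AE-log recording for unanticipated events, should be aligned at the same time.

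Cost: wording changes, one more table, and one extra CRF field if onset time is not already there. The table will include background events of prematurity under both incubators, and with 36 babies it will describe rather than test a difference.

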4.2.5 Staff feedback

All staff involved in the use of the incubator for care of the baby within, set up or cleaning will complete a questionnaire and provide any further anecdotal comments they wish to make.

5. STUDY DESIGN

The study has a prospective, multi-centre, randomised controlled, cross-over design. There will be two arms to the research. The first arm will consist of mOm incubator

care for 24 hours, followed by a further 24 hours where the subject is transferred for care to a standard incubator. The second arm will consist of 24 hours care in a standard incubator followed by 24 hours care in a mOm incubator. The care of the baby (subject) is mostly unchanged from standard incubator care, but observations may be recorded more frequently (*i.e.* hourly) for incubator displayed temperatures and some other physiological measures of clinical stability than would normally be collected in routine care for this type of clinically stable baby of at least 30 weeks GA (normally every three hours) (See Table 1). No additional blood tests or any other invasive testing or monitoring are required. The clinical research team will have full control and responsibility for the baby's care, with the ability to withdraw the baby from the study at any time for any reason if they feel the baby is clinically unstable or is adversely affected by their environment. The order of incubator type in which the baby is cared for (*i.e.* which arm of the study) before being crossed over to the alternative incubator type will be assigned at random at the point of written consent being gained and the subject therefore having been officially recruited.

Babies that are considered clinically stable from a cardio-respiratory point of view but require at least 48 hours incubator care but not requiring additional humidification will be recruited to the study from the Neonatal Unit. In practice, this will mostly be babies weighing less than approximately 1400g at 30 weeks, although some term babies may also be eligible for the study if they are being nursed in an incubator for clinical reasons.

The aim is to collect 36 completed data sets for analysis; to achieve this approximately 40 babies will be recruited; recruitment will be stopped once 36 completed data sets are available. The target is to complete recruitment within a nine-month period.

6. STUDY PROCEDURES

6.1 Recruitment

Identification and recruitment of subjects will be carried out by the attending Consultant Neonatologist and the clinical research team to whom responsibility has been delegated via the delegation of authority log.

Babies who are already being cared for in the Neonatal Unit, that meet the inclusion criteria for the study are eligible to be recruited as study subjects. For twins, consecutive enrolment will be possible if an appropriate incubator is available.

The parents/legal guardians of the baby(s) will be approached by a suitably qualified member of the clinical research team to provide written informed consent for their baby(s) to be recruited to this study. They will be given a Participant Information Sheet (PIS) to read and given the opportunity to discuss the study and ask any questions. It will be explained to them that allowing their baby to become a subject in the study is totally voluntary and if they do not agree to giving their consent, the standard care given will not be affected. If they do agree to let their baby become a subject in the study, they will be asked to sign an Informed Consent Form (ICF) of which they will be given a copy. Once written informed consent has been gained, the subject is registered on the enrolment log, considered recruited to the study and assigned a subject number.

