6.2 Procedure

There will be two arms to the protocol as detailed in section 5. The Case Report Form labelled with the appropriate subject number contains the data forms for that subject and a randomisation envelope attached inside the cover of the CRF which indicates which incubator type (standard or mOm) will be used for the baby to spend the first 24 hours in, before being switched to the alternate incubator type for a further 24 hours.

All data collected for the duration of the study will be entered in the appropriate source data (e.g. medical notes, electronic data capture systems, cleaning logs etc) and into the subject's CRF. Adverse events (AE) should be entered.

Baseline data such as length, weight, gender, core/truncal temperature (recorded at time point 0 in physiological recordings section), GA at birth, date of birth and current age of the baby will be recorded on entry to the study. Hourly observations (+/- 15 minutes) will be taken throughout the following 48 hours of incubator care, and will include temperature data displayed on the incubator, plus routine clinical observations of the baby (i.e. pulse rate, O₂ saturation and respiration rate), plus axillary temperature as per standard practice and blood pressure recorded at least once per day (See Table 1 below)

Table 1: Clinical Data Recording

Parameter	Frequency
Core/Truncal Temperature	Hourly
Pulse Rate	Hourly
Oxygen Saturation	Hourly
Respiration Rate	Hourly
Axillary Temperature	As per standard of care (usually every 2-4hrs)
Blood Pressure	As per standard of care (at least once per day)
Events (e.g. door open for feeding, care, baby removed for cuddles)	For each event record start and end time, type of activity, number of portholes/door open, any error/alarms on the incubators and any comments.

Each incubator will be individually identified by serial number for reference in CRFs, source documents (medical record/chart) and on cleaning logs. The randomisation details and the identification number of the incubators used will be recorded when the subject put into the first incubator; likewise, at the 24 hours cross-over point.

Further details about the mOm incubator can be found in the Investigator brochure (IB) filed in the ISF. For the incubator, hourly temperature readings from the digital display, time to set up, time to clean, types of cleaning performed and reasons/times when incubator opened to administer to baby's care will be recorded.

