8. STATISTICS AND DATA ANALYSIS

The primary endpoint is babies' truncal skin surface temperature variation; also termed core or central temperature. This is expected to fluctuate but remain within normal temperature limits (36.5 to 37.5 degrees Celsius). Variations from this endpoint will be analysed and compared statistically between the two arms of the study.

Thirty-six completed datasets are required for the analysis to be valid. A complete subject dataset will be deemed acceptable if 19 of the 24, once-hourly temperature observations have been recorded for each incubator type (*i.e.* 79% compliance). This degree of compliance was considered acceptable for analysis because it is still greater than the routine standard for this type of incubator care for clinically stable infants of 30 weeks GA or greater, which is often every three hours. Although data analysis will be largely descriptive, the performance of the mOm incubator will be statistically quantified by assessment of the fluctuations of babies' temperatures during each 24-hour period. It is expected that these babies' temperatures will fluctuate by around one degree Celsius, and this is normal. Thus, analysis will explore whether fluctuations for each baby keep within this bound. A 95% confidence interval will be calculated around the mean of these fluctuations within each baby for each of the two incubators. Data from 36 babies would allow such a confidence interval to be calculated to within plus or minus 0.33 of a degree if the actual mean fluctuations are around one degree (*i.e.* as normally expected) and assuming a two-sided confidence interval.

Each patient will serve as their own control. The order of incubator type used for each of the two consecutive 24-hour periods of incubator care, and therefore which study arm the subject is recruited to, will be assigned randomly. A Microsoft Excel random number generation system will be used to generate random numbers with which the arm of the study which the subject is to enter will be assigned. Each assignment will be placed in an envelope attached to each CRF already numbered with a continuous series subject number.

Baseline demographic factors of the study subjects will be summarised. For continuous variables, such as weight, the mean, standard deviation, median and range will be presented. For categorical variables, such as gender, the proportion of subjects in each category will be presented.

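### Both twins of a pair may be enrolled, but the ±0.33 °C precision and the per-incubator 95% CIs treat 36 babies as independent; if correlated pairs enter, the intervals will be somewhat too narrow, and no explicit sibling identifier is listed.

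*Combined protocol and SAP*

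**What the plan says.** Section 6.1 (Recruitment) allows siblings into the trial and sets no limit on their number: "For twins, consecutive enrolment will be possible if an appropriate incubator is available".

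Section 8 (Statistics and Data Analysis) fixes the sample size in babies: "Thirty-six completed datasets are required for the analysis to be valid". The planned interval is described as follows: "A 95% confidence interval will be calculated around the mean of these fluctuations within each baby for each of the two incubators". Its precision is given as: "Data from 36 babies would allow such a confidence interval to be calculated to within plus or minus 0.33 of a degree", on the condition "if the actual mean fluctuations are around one degree" and "assuming a two-sided confidence interval". Section 8 then makes the interval for each incubator type the measure for judging whether the mOm incubator performs as well as the standard one. It names no term for family, incubator unit or site.

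Section 6.2 (Procedure) lists baseline items by way of example. They include date of birth and gestational age at birth, but no multiple-birth or pair code. The site enrolment log in section 11 holds name, hospital number and date of birth against subject number. On incubators, section 6.2 says: "Each incubator will be individually identified by serial number for reference in CRFs". Section 8 gives these serial numbers no role.

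**The concern.** Twins share gestational age, and usually also unit, staff and much of their clinical background, so their temperature fluctuations may well be alike. Two alike babies carry less information than two unrelated ones. An interval that counts them as two independent observations then claims more precision than it has.

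Using each baby as its own control does not deal with this. It handles the two periods within a baby, not the link between babies. In a within-baby difference between incubators, effects shared by siblings would partly cancel. The plan instead relies on a separate interval for each incubator type, where they do not cancel.

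There is also a practical side. A pair code is easy to record at enrolment and harder to recover later. Section 10 makes the subject number the only identifier, and section 11.2 has results anonymised before analysis. Whether date of birth would remain available to the analyst is not settled by the text.

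**Working it through.** **Inputs from the documents.** n = 36 babies; two-sided 95% interval; stated half-width 0.33 °C; mean fluctuation about 1 °C (all section 8). Twins allowed, no cap (section 6.1).

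**Inputs not in the documents.** The SD of the fluctuations, the number of twin pairs, and the within-pair correlation. All three are assumed below.

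**Step 1: reproduce the plan's figure.** Half-width = 1.96 × SD / √n. With SD = 1, this is 1.96 × 1 / √36 = 0.327, which rounds to 0.33. Working backwards, 0.33 implies SD = 0.33 × 6 / 1.96 = 1.01. The figure is thus recovered with 36 independent babies, no allowance for clustering, and an SD of about 1. Section 8 states a mean of about one degree but no SD.

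**Step 2: allow for twins.** With k complete pairs among n babies and within-pair correlation ρ, the variance of the mean is (SD²/n) × (1 + 2kρ/n). The design effect is therefore DE = 1 + (2k/36) × ρ. The correct half-width is 0.327 × √DE, the effective sample size is 36/DE, and the true coverage of the unadjusted interval is 2Φ(1.96/√DE) − 1.

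| Pairs (assumed) | ρ (assumed) | DE | Half-width, °C | Effective n | Coverage of unadjusted 95% CI |
|---|---|---|---|---|---|
| 0 | any | 1.000 | 0.327 | 36 | 95.0% |
| 1 | 0.1 | 1.006 | 0.328 | 35.8 | 94.9% |
| 1 | 0.5 | 1.028 | 0.331 | 35.0 | 94.7% |
| 2 | 0.3 | 1.033 | 0.332 | 34.8 | 94.6% |
| 4 | 0.3 | 1.067 | 0.337 | 33.8 | 94.2% |
| 4 | 0.5 | 1.111 | 0.344 | 32.4 | 93.7% |
| 6 | 0.5 | 1.167 | 0.353 | 30.9 | 93.0% |
| 8 | 0.7 | 1.311 | 0.374 | 27.5 | 91.3% |

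Worked example, 6 pairs at 0.5: DE = 1 + (12/36) × 0.5 = 1.167; 0.327 × √1.167 = 0.353.

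**Step 3: dependence on the SD.** The absolute figures scale with the assumed SD, but the proportional widening does not: √1.167 = 1.08, or 8%, for 6 pairs at 0.5, and √1.311 = 1.145, or 14.5%, for 8 pairs at 0.7. With SD = 0.5 (assumed), the base half-width would be 0.163, and 0.187 at the largest design effect shown.

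**Step 4: is there slack in recruitment?** At SD = 1, a half-width of 0.33 needs (1.96/0.33)² = 35.3 independent babies. Multiplied by DE and rounded up, this becomes 40 completed babies for 4 pairs at 0.5, and 42 for 6 pairs at 0.5. Section 5 does plan a surplus ("to achieve this approximately 40 babies will be recruited"), but that is to yield 36 completed sets, and recruitment stops once those exist. Precision lost to pairing would not be recovered.

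**The case against.** The strongest reply is that the effect is conditional and small. It needs at least one complete pair and a positive correlation; without both, nothing is lost. Four pairs at a correlation of 0.3 move the half-width to 0.337, less than the change from a normal to a t quantile with 35 degrees of freedom (0.338). The 0.374 case needs 16 of the 36 babies to be twins with a correlation of 0.7, and nothing in the documents supports either figure. The analysis is described as largely descriptive and sets no numerical margin, so a shift of this size crosses no stated threshold. The unstated SD matters more than the twins. All of this stands, and it limits the weight of the point.

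It can also be said that siblings are not untraceable: date of birth and gestational age are collected, and the site log can confirm a match. That is right, and a reader should not infer that no recorded item could link siblings. What is missing is an explicit identifier that is sure to reach the analysis data; a shared birth date alone does not prove kinship.

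A reader might go further and infer that reuse of incubators makes the intervals much too narrow, or that a badly performing mOm unit would vanish in the average. The documents do not support either. Timing of cleaning between subjects implies reuse, but neither the number of units nor any correlation between babies nursed in the same unit is given, so no size can be put on it. Unit performance is already captured: serial numbers, hourly set and actual incubator temperatures, alarms and malfunctions are all recorded. What is absent is a tabulation by unit.

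**Conclusion.** The point holds in conditional form. The plan admits twin pairs without limit, counts 36 independent babies in both its precision statement and its decision intervals, and lists no explicit sibling identifier. If pairs are enrolled and their fluctuations are positively correlated, the per-incubator intervals will be somewhat too narrow.

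Taking the SD of about 1 that 0.33 implies, the half-width rises from 0.327 to about 0.33–0.35 for 1 to 6 pairs with a correlation of up to 0.5, and to 0.37 for 8 pairs at 0.7. Pair counts, correlations and SD are assumptions. It would be too strong to say that the intervals are certainly too narrow: the documents do not say how many pairs will enter or how alike they will be. This is a modest defect, worth correcting because the correction is easy and the pair code is best captured at enrolment.

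**What to change.** 1. Add a multiple-birth and pair identifier to the CRF baseline page, and carry it into the anonymised analysis data as a code that reveals no identity.
2. In section 8, compute the intervals with family as the cluster, using either a random intercept for family or a cluster-robust standard error with a small-sample correction. Add a sensitivity analysis that keeps one twin per pair, with the rule for choosing the twin fixed in advance.
3. State beside the 0.33 that it assumes independent babies, and give the SD on which it rests.
4. As a minor descriptive addition, tabulate fluctuations by incubator serial number for both mOm and standard incubators. The data are already collected.

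The cost is one CRF field and a few sentences in section 8, with no extra babies or procedures. The downside is slightly wider intervals if correlated pairs are enrolled.
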